13.2.2 Secondary endpoints

Time to recurrence

TTR will be calculated from surgery until recurrence or death due to colon cancer. Patients not experiencing an event or patients who died due to other reasons before experiencing an event will be censored at the date of the last available tumor assessment.

Overall survival

OS will be calculated from surgery until death from any cause. Patients not experiencing an event will be censored at the last date they were known to be alive.

Cancer-specific survival

CSS will be calculated from surgery until death due to colon cancer, whether due to the original tumor or to a second primary same cancer. Patients who died due to other reasons will be censored at the time of death. All other patients will be censored at the last date they were known to be alive.

Adverse events

AEs will be assessed according to NCI CTCAE v4.0.

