15 STATISTICAL CONSIDERATIONS

15.1 Sample size estimation

- Software package: East 6.2
- Number of treatment arms: 2
- Type of design: parallel design
- Trial intention: superiority
- Statistical test: One-sided log-rank test
- Null hypothesis: hazard ratio (HR) 1.0
- Alternative hypothesis: HR 0.456 (corresponding to a 3-year DFS of 70% in the placebo arm and 85% in the aspirin arm assuming constant hazards). This hazard ratio is based on the two published retrospective studies: The hazard ratio for cancer-specific survival in the study by Liao et al. [13] was 0.18, the hazard ratio in the study by Domingo et al. [14] for recurrence was 0.11. Therefore, the assumed hazard ratio of 0.456 in this trial represents a conservative estimate. The assumption of a 3-year DFS of 70% in the placebo arm was based on several studies [4, 13, 14, 26] as well as analyses of the SEER data base (<http://seer.cancer.gov/data/>) and analyses performed on data of the Cantonal Hospital St. Gallen.
- Type I error: 5%
- Power: 80%
- Randomization ratio: 2:1
- Number of interim analyses for the primary endpoint: Two
- Timing of interim analyses: after 25% (11) and 50% (22) of the events, the first is expected after approximately 2.4 years of accrual and the second after approximately 0.5 years of follow-up.
- Stopping boundary for benefit/futility: Lan-DeMets error spending function in spirit of the O'Brien & Fleming boundary [27, 28].
- Expected accrual rate: 60 patients per year
- Expected accrual time: 3 years
- Expected follow-up time until primary analysis: 3 years
- Expected proportion of lost to follow-up: 20%. This is based on various studies assessing aspirin intake [29-31].
- Required number of events: 43
- Sample size: 185 (123 in the aspirin group, 62 in placebo group)

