15.3 Statistical analyses

The primary analysis will take place once the 43rd DFS event has taken place or at the latest after 3 years from the date of surgery of the last included patient.

All efficacy endpoints will be analyzed based on the full analysis population. Supportive analyses based on the PP population will be performed. All safety endpoints will be analyzed based on the safety population. Subgroup analyses for all stratification factors except country are planned for the primary endpoint. All time-to-event endpoints shall have the median value of each treatment group estimated using the Kaplan-Meier method, along with a 95% confidence interval. The number of events of each endpoint shall be presented descriptively by frequency and percentage by treatment arm. The treatment effect will be assessed using Cox regression models with the treatment arm as independent variable and the stratification factors as strata. Cox regression models will also be used to investigate the potential effects of other factors (e.g. chemotherapy given and concomitant therapy) on selected endpoints. Subgroup analyses may be performed for these factors. For the primary analysis, patients who were unblinded before experiencing an event will be censored at the date of the last available tumor assessment before unblinding. A supportive analysis will be performed in which the unblinding will not be considered.

Categorical variables will be summarized with frequency and percentage and may be compared between arms by chi-square tests or Fisher's exact tests. Continuous variables will be summarized using median and range and may be compared between arms by t-tests or Wilcoxon rank sum tests.

Laboratory values will be expressed as the absolute values and as grading according to NCI CTCAE v4.0 by treatment arm. AE grading shall be presented by type, grade, and relation showing frequency and percentage of the within-patient worst grades by treatment arms. In addition, grade ≥ 3 AEs and AEs with relation to treatment ≥ 3 will be summarized separately.

Full analysis details will be outlined in the statistical analysis plan (SAP).

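### TTR and CSS are set up for Kaplan-Meier with other-cause deaths censored; as a summary of absolute risk this overstates recurrence and colon-cancer death, and cumulative incidence should replace it

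*Combined protocol and SAP*

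**What the plan says.** Section 13.2.2 handles a death from another cause differently in its two cancer-specific endpoints. For CSS, "Patients who died due to other reasons will be censored at the time of death". For TTR, "patients who died due to other reasons before experiencing an event will be censored at the date of the last available tumor assessment". In both cases the death ends follow-up as a censored observation.

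Section 15.3 sets the summary: "All time-to-event endpoints shall have the median value of each treatment group estimated using the Kaplan-Meier method", with a 95% confidence interval. It also asks for the count and percentage of patients with each event by arm. For the comparison, "The treatment effect will be assessed using Cox regression models with the treatment arm as independent variable and the stratification factors as strata".

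The protocol does not mention competing risks or cumulative incidence. Section 15.3 adds: "Full analysis details will be outlined in the statistical analysis plan (SAP"). No separate SAP text is in the document supplied, so the point concerns what the protocol states.

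**The concern.** Kaplan-Meier assumes that a censored patient has the same future risk as those who stay under observation. That is reasonable for someone still alive at the data cut. It cannot hold for someone who has died, whose future risk of recurrence or colon-cancer death is zero. One minus Kaplan-Meier then estimates risk in a hypothetical population where nobody dies of anything else, and this exceeds the proportion of patients who actually have the event.

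Other-cause deaths are to be expected here. Section 6.1 sets no upper age limit and admits performance status 0-2. Deaths from a second cancer other than colon cancer also fall into the censored group for both endpoints.

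TTR has a further weakness: the competing death is not placed at its own date. CT is yearly and, after month 24, clinic visits are six-monthly, so the last tumor assessment may precede death by months.

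At stake is how readers understand the absolute risk of recurrence and of colon-cancer death. The test of the primary hypothesis is not at stake.

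**Working it through.** **Design figures.** The protocol gives no planning figure for TTR, CSS or other-cause death, so the check starts from the DFS assumption in section 15.1: "HR 0.456 (corresponding to a 3-year DFS of 70% in the placebo arm and 85% in the aspirin arm assuming constant hazards").

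- Placebo hazard: -ln(0.70)/3 = 0.1189 per year.
- Aspirin hazard: -ln(0.85)/3 = 0.0542 per year.
- Ratio: 0.0542/0.1189 = 0.456, as stated.

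The 43 events also reproduce. With one-sided 5% and 80% power, (1.645 + 0.842)² = 6.183 and (ln 0.456)² = 0.617. The 2:1 allocation is offset by the hazard ratio, so expected events split about 51:49 between arms. This gives 6.183/(0.25 × 0.617) = 40.1. An inflation of 1.078 for the two interim looks, assuming O'Brien-Fleming-type spending for both efficacy and futility, gives 43.2. The hazards are therefore usable as inputs.

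**Formulas.** Take constant hazards, *l* for the cancer event and *h* for other-cause death, at time *T*:

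- Kaplan-Meier risk = 1 - exp(-*lT*)
- Cumulative incidence = *l*/(*l* + *h*) × [1 - exp(-(*l* + *h*)*T*)]

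**Assumptions.** DFS hazards stand in for TTR hazards. The rate *h* is not in the document; 0.01-0.04 per year is assumed, at first equal in both arms. Censoring is taken at death; the earlier TTR date is not modelled.

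**Result at 3 years (percent):**

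| *h* per year | Placebo KM | Placebo CIF | Excess | Aspirin KM | Aspirin CIF | Excess |
|---|---|---|---|---|---|---|
| 0.01 | 30.0 | 29.6 | 0.4 | 15.0 | 14.8 | 0.2 |
| 0.02 | 30.0 | 29.2 | 0.8 | 15.0 | 14.6 | 0.4 |
| 0.03 | 30.0 | 28.8 | 1.2 | 15.0 | 14.4 | 0.6 |
| 0.04 | 30.0 | 28.4 | 1.6 | 15.0 | 14.2 | 0.8 |

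Example, placebo at *h* = 0.02: 0.1189/0.1389 × [1 - exp(-0.1389 × 3)] = 0.292, against 0.300.

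**Effect on the median.** One minus Kaplan-Meier reaches 50% at ln 2/*l*, which is 5.8 years on placebo and 12.8 on aspirin. Cumulative incidence reaches 50% at -ln[1 - 0.5(*l* + *h*)/*l*]/(*l* + *h*). At *h* = 0.02 this is 6.3 and 15.6 years. The Kaplan-Meier median comes too early.

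**Sensitivity to the stand-in.** DFS already counts all deaths, so using its hazard for *l* and then adding *h* counts other-cause deaths twice. If *l* is instead the DFS hazard minus *h*, the 3-year excess over the same range is 0.4-1.2 points on placebo and 0.2-0.3 on aspirin. For example, at *h* = 0.04 on placebo, *l* = 0.0789, Kaplan-Meier gives 21.1% and cumulative incidence 0.0789/0.1189 × 30.0% = 19.9%, an excess of 1.2. Second cancers are still included in *l*.

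**Is it unequal by arm?** With *h* = 0.02 in both arms, the excess is 0.83 points on placebo and 0.43 on aspirin. That is about 2:1 in points but nearly equal in relative terms (0.83/29.17 = 2.8%; 0.43/14.57 = 3.0%). With *h* = 0.02 on placebo and 0.01 on aspirin it is 0.83 and 0.22. With 0.02 and 0.04 it is 0.83 and 0.84, so the gap closes. With 0.01 and 0.04 it reverses: 0.42 and 0.84.

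**The case against.** The strongest counter-argument is that the plan never promises the biased quantity. Section 15.3 asks for a Kaplan-Meier median and crude event percentages. The crude percentages carry no Kaplan-Meier inflation, and no landmark recurrence rate or absolute risk difference is called for. This stands, and it limits the point. It does not remove it. The median comes from the same estimate, and it may well not be reached: accrual began in Q2 2016 and follow-up ends in Q4 2023 (section 5) or Q3 2024 (section 12.3), against medians of 5.8 and 12.8 years for DFS and later ones for TTR and CSS. Curves and landmark rates are then the natural substitute, and there the bias shows. That last step is an inference about reporting.

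A reader might infer that the treatment comparison is wrong. The document does not support this. A Cox model with other-cause deaths censored estimates the cause-specific hazard ratio, a legitimate effect measure.

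A reader might also infer that the bias is unequal by arm, or that the arm difference is overstated. Aspirin could plausibly shift other-cause death either way: section 8.1.1 notes its use in cardiovascular prevention, and section 2.4 cites gastrointestinal hemorrhage of 2.47% against 1.42%. But the protocol gives no cause-specific death rates by arm, and the calculations show the gap widening, closing or reversing with the rates assumed. The inequality in the equal-rate table comes entirely from the assumed hazard ratio.

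Two further objections have weight. The unseen SAP may already specify a competing-risk method. And censoring TTR at the last tumor assessment matches the DFS rule for patients without an event; however, DFS counts a death as an event, so that rule is never applied there to a patient who has died.

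**Conclusion.** The point holds as a minor one about description. As the protocol stands, the Kaplan-Meier summary of TTR and CSS overstates absolute risk whenever other-cause deaths occur. The direction is certain. At the 3-year design horizon the size is about 0.4-1.6 points on placebo and 0.2-0.8 on aspirin. This rests on constant hazards, DFS hazards as an approximate stand-in for TTR, and an assumed other-cause death rate of 1-4% per year. Removing the double count of deaths lowers the upper ends to about 1.2 and 0.3. No figure is computed for CSS, because the protocol gives no colon-cancer death rate.

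Whether the excess differs by arm, and in which direction, cannot be settled from the document. DFS and OS count all deaths, so the primary conclusion does not depend on this point.

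**What to change.** In section 15.3 or the SAP, for TTR and CSS only:

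- Replace the Kaplan-Meier summary with Aalen-Johansen cumulative incidence by arm, with 95% confidence intervals and other-cause death as the competing event.
- Enter that death at its actual date for both endpoints, including TTR. Patients alive without an event keep their present censoring dates.
- Tabulate other-cause deaths by arm, so that readers can see how much the competing event matters and whether it is balanced.
- Keep the stratified Cox model and label its result a cause-specific hazard ratio.

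The cost is a few lines of text and a small amount of extra analysis. The endpoint definitions already require cause and date of death, so no new data are needed. The primary analysis does not change.

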14 DOCUMENTATION

14.1 CRFs and reports

CRFs specifically created for this trial are used for documentation. It is very important to adhere to the schedule of visits prescribed in the protocol for all patients.

The CRFs have to be completed online (www.sakk.ch/edc) in a timely manner. The data should be entered into the electronic eCRFs within a month from the visit or medical examination. All eCRFs needed for the corresponding visit will be displayed automatically in the web-based electronic data capture (EDC) system for the SAKK 41/13-Aspirin trial.

Sites must use a patient identification list in order to allow identification of a patient. This list must be kept at the site in the investigator's file.

14.2 Notes for special handling of CRFs

Eligibility CRF:

- The completed form ER in the web-based EDC system has to be printed and signed by the investigator. **A certified copy of the signed form has to be sent to the responsible CPM by mail or fax within one month after the patient's inclusion.** The original signed form is kept at the site in the investigator's file.
- If it is not possible to enter the eligibility form online for technical reasons, complete the paper version of the eligibility CRF and fax it in due time to the SAKK CC, which will perform the registration/randomization of the patient (see also section 7.2).

SAE and pregnancy report forms:

- Trial-specific SAE report forms and trial-specific pregnancy report forms have to be submitted **by email** to the SAKK safety office within 24 hours of becoming aware of the SAE or pregnancy (see also section 11 for SAE reporting and pregnancy reporting). Originals of SAE and pregnancy reports are kept at the site in the investigator's file.

14.3 Source data

Additionally to other source data, the following data entered directly onto trial documents are considered to be source data:

- patient screening and enrollment list
- patient identification list
- drug inventory logs
- patient diary
- PIK3CA screening results cover letter

The source of original records and all data considered to be source data are defined in the SDL form (source data location form).

15 STATISTICAL CONSIDERATIONS

15.1 Sample size estimation

- Software package: East 6.2
- Number of treatment arms: 2
- Type of design: parallel design
- Trial intention: superiority
- Statistical test: One-sided log-rank test
- Null hypothesis: hazard ratio (HR) 1.0
- Alternative hypothesis: HR 0.456 (corresponding to a 3-year DFS of 70% in the placebo arm and 85% in the aspirin arm assuming constant hazards). This hazard ratio is based on the two published retrospective studies: The hazard ratio for cancer-specific survival in the study by Liao et al. [13] was 0.18, the hazard ratio in the study by Domingo et al. [14] for recurrence was 0.11. Therefore, the assumed hazard ratio of 0.456 in this trial represents a conservative estimate. The assumption of a 3-year DFS of 70% in the placebo arm was based on several studies [4, 13, 14, 26] as well as analyses of the SEER data base (<http://seer.cancer.gov/data/>) and analyses performed on data of the Cantonal Hospital St. Gallen.
- Type I error: 5%
- Power: 80%
- Randomization ratio: 2:1
- Number of interim analyses for the primary endpoint: Two
- Timing of interim analyses: after 25% (11) and 50% (22) of the events, the first is expected after approximately 2.4 years of accrual and the second after approximately 0.5 years of follow-up.
- Stopping boundary for benefit/futility: Lan-DeMets error spending function in spirit of the O'Brien & Fleming boundary [27, 28].
- Expected accrual rate: 60 patients per year
- Expected accrual time: 3 years
- Expected follow-up time until primary analysis: 3 years
- Expected proportion of lost to follow-up: 20%. This is based on various studies assessing aspirin intake [29-31].
- Required number of events: 43
- Sample size: 185 (123 in the aspirin group, 62 in placebo group)
- Number needed to screen: 1850 assuming 17% PIK3CA mutations in colorectal cancer patients; estimate of 17% is based on New England Journal of Medicine publication [13]. PIK3CA mutations in colorectal cancer patients are described between 15% and 20% in the literature. The rate of PIK3CA mutation is relatively lower in rectal cancer (approximately 8%, [22]) compared to colon cancer. Therefore, by excluding rectal cancer patients, the estimate of a PIK3CA mutation rate of 17% is conservative. However, as not all the mutated patients will be included in the trial due to patient's wish, ineligibility discovered after PIK3CA screening, etc., it is assumed that 10% of all screened patients will be finally randomized in the trial.

Note: These calculations are based on the formula for the log-rank test. Due to the asymptotic equivalence of the test statistic of the Cox regression model without covariates and the log-rank test statistics under the assumed model, the sample size calculation holds also true for the unadjusted Cox regression model. It can be expected that inclusion of the stratification factors in the analysis will further increase the power as compared to the above calculations that are based on the Cox regression model without covariates.

15.2 Interim efficacy analyses

Two interim efficacy analyses are planned, the first after 25% (11) of the events expected after approximately 2.4 years of accrual and the second after and 50% (22) of the events, expected after approximately 0.5 years of follow-up. The accrual will not be suspended while waiting for the interim results. In case of a higher accrual rate than expected, the time point and number of events for the interim analysis may be adapted accordingly. The critical values for early stopping will be obtained using the Lan-DeMets error spending function in spirit of the O'Brien & Fleming boundary.

The two interim analyses were planned to allow the trial to stop early if the beneficial effect of aspirin is higher than the HR of 0.45 that was assumed for the sample size calculations and is a conservative estimate compared to the results from the two published retrospective studies (HR 0.11 in Domingo et al [14] and HR 0.18 in Liao et al [13]).

At the first interim analysis stopping for efficacy would be possible with a HR of 0.11 or lower and at the second interim analysis with a HR of 0.34 or lower. The proportion of patients lost to follow-up without reaching the primary endpoint will be assessed at the first interim analysis and if it is higher than 20% the sample size may be re-estimated in order to reach the required number of events in a reasonable time.

The unblinded results of the interim efficacy analysis will be presented to an independent data monitoring committee (IDMC) appointed by the SAKK board. The SAKK board will decide on the continuation/modification/early stopping of the trial based on the recommendations of the IDMC.

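### The hazard-ratio stopping thresholds in section 15.2 (0.11 and 0.34) do not match the plan's own spending rule under 2:1 randomisation, which gives about 0.09 and 0.32

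*Combined protocol and SAP*

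**What the plan says.** Section 15.1 gives the design inputs: "Statistical test: One-sided log-rank test", a 5% type I error, "Randomization ratio: 2:1" and "Required number of events: 43". The interim looks fall "after 25% (11) and 50% (22) of the events". The boundary is a Lan-DeMets spending function of O'Brien-Fleming type.

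Section 15.2 repeats that the critical values come from that function. It gives numerical thresholds only as hazard ratios. Its figure for the earlier look reads: "At the first interim analysis stopping for efficacy would be possible with a HR of 0.11 or lower". The companion figure, for the look at 22 events, is worded "at the second interim analysis with a HR of 0.34 or lower". It prints no z or p boundary. It also allows the timing and event count of the interim analysis to be adapted if accrual is faster than expected. Unblinded interim results go to an independent data monitoring committee, and the sponsor's board decides on its recommendation.

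**The concern.** A critical value on the z scale becomes a hazard ratio only through the information per event. Under the null hypothesis that information is r(1−r), where r is the share allocated to aspirin: 1/4 for equal allocation and 2/9 for 2:1. The printed thresholds fit 1/4, although the trial is 2:1.

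The hazard ratios are the only stopping figures given in numbers, so a reader could take them as the rule. They are more lenient than the spending function permits. The value 0.11 also equals the hazard ratio that section 15.2 cites from one of the two retrospective studies. The text therefore suggests that an effect of that size would just be enough to stop at the first look. Under the 2:1 conversion it would not be.

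**Working it through.** **Inputs (sections 15.1 and 15.2).** One-sided log-rank test; α = 0.05, read as one-sided; 43 events in total; looks at D = 11 and 22, so t = 11/43 = 0.256 and 22/43 = 0.512; allocation 2:1.

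**Step 1: boundaries.** Cumulative alpha spent is α(t) = 2[1 − Φ(1.960/√t)], which gives 0.000107, 0.00614 and 0.05. Recursive integration gives:

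| Look | z | nominal one-sided p |
|---|---|---|
| 11 events | 3.703 | 0.0001 |
| 22 events | 2.506 | 0.0061 |
| 43 events | 1.664 | 0.048 |

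**Step 2: reproduce the plan's figures.** The conversion is HR = exp(−z/√I). With I = D/4:
- 11 events: exp(−3.703/√2.75) = 0.107, which rounds to the printed 0.11.
- 22 events: exp(−2.506/√5.5) = 0.343, which rounds to the printed 0.34.

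**Step 3: use the planned allocation.** With I = 2D/9:
- 11 events: exp(−3.703/√2.444) = 0.094.
- 22 events: exp(−2.506/√4.889) = 0.322.

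**Step 4: what the printed values give under 2:1.**
- HR 0.11 at 11 events: z = −ln(0.11) × √2.444 = 3.45, p = 0.00028, against 3.70 and 0.000107. The ratio is 2.6. Rounding does not explain the gap: any HR from 0.105 to 0.115 gives z between 3.52 and 3.38.
- HR 0.34 at 22 events: z = −ln(0.34) × √4.889 = 2.39, against 2.51.

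**Step 5: event counts.** With risk sets held at 2:1, the score statistic is z = (2D/3 − x)/√(2D/9), where x is the number of aspirin events.
- 2 v 9 at 11 events: crude HR (2/2)/9 = 0.111, z = 3.41, not across.
- 1 v 10 at 11 events: crude HR 0.05, z = 4.05, across.
- 9 v 13 at 22 events: crude HR (9/2)/13 = 0.346, z = 2.56, just across 2.51. In event counts, therefore, 0.34 lies close to the log-rank boundary.

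**Step 6: simulation under the null at 11 events.** The assumptions, which are not in the documents, were 123:62 patients, uniform accrual over about 3.1 years, 3-year DFS of 70% in both arms and no drop-out. A Cox HR of 0.11 or lower occurred with probability 0.00045, against 0.00024 for crossing z = 3.703. A separate simulation gave 0.00051 against 0.00027. Both ratios are about 1.9. The crossing rate itself exceeds the nominal 0.000107, so normal theory is rough at 11 events.

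**Step 7: overall one-sided alpha (normal theory, final z unchanged at 1.664).** Replacing 3.70 by 3.45 at the first look moves alpha from 0.05000 to 0.05005. Replacing both interim boundaries by the printed hazard ratios gives 0.0511.

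**Sensitivity.** With t set to exactly 0.25 and 0.50 (events 11 and 22), D/4 gives 0.104 and 0.339, and 2D/9 gives 0.091 and 0.317. With two-sided 5%, D/4 gives 0.076 and 0.287, and 2D/9 gives 0.065 and 0.266. Adding futility boundaries leaves the interim efficacy values unchanged. No 2:1 variant reproduces the printed pair.

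**The case against.** The strongest defence is that section 15.2 makes the spending-function critical values operative and uses the hazard ratios only to illustrate what would be possible. Because that section allows the event counts to change, fixed hazard ratios could not be the rule anyway. This stands. A reader might infer that the committee was handed a faulty hazard-ratio rule and that type I error is inflated, but no section says so. If the z boundary is applied, error is controlled and only the printed figures are wrong.

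A reader might also infer that the design was calculated as if allocation were 1:1. The documents do not show this. At the design hazard ratio of 0.456, 2:1 arms yield nearly equal expected event numbers (aspirin share 0.49 to 0.51), so a variance-under-the-alternative setting would also give D/4. That may explain where the figures came from, but it does not validate them. The log-rank type I error is governed by the null variance, and at a hazard ratio of 0.11 the events split about 2 v 9, not evenly.

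A third tempting reading is that the trial could not stop at 0.11, or only with 0 or 1 aspirin events. This is too strong. Risk sets drift, and about 14% to 16% of simulated 2 v 9 splits crossed the log-rank boundary. With risk sets fixed at 2:1, a 2 v 9 split is 0.111, already above 0.11, so both criteria then select the same outcomes. The discrepancy remains once risk sets vary, as the 1.9-fold ratio shows.

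Nor is a 13-fold excess supportable. It sets an exact binomial probability (0.0014 for 2 or fewer of 11) against a normal-theory 0.000107, and it counts 2 v 9 splits that do not reach 0.11.

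Finally, accrual and treatment ended early for financial reasons with 113 of 185 patients randomised, and the documents do not say whether any interim look was held. The prospective consequence is limited.

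**Conclusion.** The point holds as a minor numerical inconsistency. The printed thresholds of 0.11 and 0.34 do not correspond to the Lan-DeMets boundaries for the planned one-sided 5% log-rank test with 2:1 allocation; the corresponding values are about 0.09 and 0.32. If 0.11 were used as the rule, first-look alpha would be about 2 times (simulation) to 2.6 times (normal theory) what the boundary allows. The excess in overall one-sided alpha is about 0.0001 or less from the first look, and about 0.001 if both hazard ratios were used.

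This rests on reading the 5% as one-sided, on looks at exactly 11 and 22 of 43 events, on the null variance of the log-rank test, and on a large-sample conversion that is approximate at 11 events. Why the figures match D/4 remains unknown.

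**What to change.** In section 15.2, or in the SAP to which section 15.3 defers full details:

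- State the efficacy boundaries on the z or p scale and name them as the operative rule: z = 3.70 (p = 0.0001) at 11 of 43 events, z = 2.51 (p = 0.0061) at 22 of 43, and z = 1.66 (p = 0.048) at 43. Say that they are recomputed from the spending function at the actual event counts.
- Either remove the hazard-ratio figures or restate them as approximate 2:1 values, about 0.09 and 0.32.
- If any interim look was held, derive the final critical value on the same scale, from the event counts at that look.

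The cost is a few lines of wording and numbers. The design, the event target and the data collected do not change.
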